9.4. Screen Failures

Screen failures are defined as participants who consent to participate in the clinical study but are not subsequently enrolled in the study. A minimal set of screen failure information is required to ensure transparent reporting of screen failure participants to meet the Consolidated Standards of Reporting Trials publishing requirements and to respond to queries from regulatory authorities. Minimal information includes screen failure details, eligibility criteria, and any SAEs.

Individuals who do not meet the criteria for participation in this study (screen failure) may be re-screened. Re-screening will be allowed within the recruitment period for the study. Re-screened participants should be assigned a new screening number.

9.5. Participant Replacement

Participants who are enrolled but who do not receive any IP will be replaced and the replacement participant will be assigned the same treatment as the participant they are replacing.

Participants who discontinue the study at any time after the initiation of dosing will be retained in the Safety Population, however additional participants may be recruited at the discretion of the Sponsor to obtain an evaluable PK Population and/or Metabolite Population.

9.6. Participant Withdrawal Criteria

In accordance with applicable regulations, a participant has the right to withdraw from the study, at any time and for any reason, without prejudice to their future medical care. If a participant withdraws consent, the date and reason for consent withdrawal should be documented. Participant data will be included in the analysis up to the date of the withdrawal of consent.

A participant must be removed from the study at any time, if any of the following criteria is met:

- Participant voluntarily withdraws consent,
- Participant cannot meet the dosing compliance specified the [Section 10.5](#),
- Any other clinical AE, medical condition, or situation arises, that in the opinion of the Investigator it would not be in the best interest of the participant to continue participation.

If a participant is withdrawn because of an AE, the Investigator must arrange for the participant to have appropriate follow-up care until the AE is resolved or has stabilized. Unresolved AEs will be followed until the last scheduled Follow-up/ET visit or until the Investigator and MM determine that further follow-up is no longer indicated.

If a participant is withdrawn due to a lack of dosing compliance, a clear reason for not completing the treatment must be recorded. The collection of PK samples post-dose will not be

performed. Before discharge, safety assessments post-dose on Day 1 will be completed and an Early Termination visit will be planned.

If a participant asks or decides to withdraw from the study, all efforts will be made to complete and report the observations, especially those related to the listed primary and secondary objectives, as thoroughly as possible up to the date of withdrawal. A clear and concise reason for withdrawal will be identified and recorded on the appropriate eCRF, along with the date of withdrawal.

10. TREATMENTS

10.1. Treatments Administered

10.1.1. Investigational Product

CBL-514 is a lipolysis injection product developed by Caliway Biopharmaceuticals Co., Ltd. CBL-514 is constituted by curcumin and *trans*-resveratrol.

CBL-514 is manufactured in compliance with Good Manufacturing Practice (GMP) regulations.

CBL-514 should be stored at 4°C, with an allowed temperature range of between 2°C and 8°C.

Table 6: CBL-514 Product Details

Name	CBL-514
Active Ingredients	Curcumin and trans -resveratrol
Dosage form	Subcutaneous Injection, [REDACTED] of CBL-514, 20 mL/vial
Pharmacological category	D11AX other dermatological

10.1.2. Reference Products

Not applicable.

10.2. Dosage and Treatment Periods

All 10 participants enrolled in the study will receive a single course of treatment with CBL-514 800 mg on the abdomen (administered as multiple subcutaneous injections) on Day 1 only. The IP administration should be completed within 60 minutes.

In order to reach the maximal CBL-514 dose of 800 mg while limiting the number of injections, [REDACTED].

The dosing scheme is presented in [Table 7](#).

Table 7: Dosing Scheme

Treatment Area	Dose level (mg/cm ²)	Injection volume per 7.5 cm ² grid (mL)	Administration			
			No. of injections	Total injection volume (mL)	Total CBL-514 (mg)	
Abdomen	2.0	[REDACTED] [REDACTED]	[REDACTED]	160	800	Curcumin [REDACTED]
						Resveratrol [REDACTED]

10.3. Method of Assigning Participants to Treatment

The study has an open-label and single course design. All 10 participants will receive CBL-514 at the same dose ([Table 7](#)).

Each participant will be provided with a unique screening number following documentation of informed consent. Participants who withdraw from the study, for any reason, without completing all necessary screening assessments will be considered screen failures (see [Section 9.4](#)).

10.4. Concomitant Medications

All medications*, including OTC medications, and dietary supplements, taken during the 6 months prior to the Screening visit will be recorded and reviewed by the Investigator to determine whether the participant is suitable for inclusion in the study.

The use of any other IP or investigational medical device within 4 weeks prior to Screening is prohibited. Additional restrictions relating to prior and concomitant medication use are outlined in [Section 9.2](#) and [Section 9.3](#), respectively.

All medications*, including OTC medications, and dietary supplements, taken by participants during the course of the study will be recorded in the eCRF and coded using the most current World Health Organization (WHO) drug dictionary available. Prior and concomitant medications will be listed by participant and summarized by anatomical therapeutic chemical (ATC) and Preferred Term (PT).

*Medications to be reported in the eCRF are concomitant prescription medications, OTC medications, and non-prescription medications. For this protocol, a prescription medication is defined as a medication that can be prescribed only by a properly authorized/licensed clinician.

A dietary supplement is a product intended for ingestion that contains a “dietary ingredient” intended to add further nutritional value to the diet. A “dietary ingredient” may be one, or any combination, of the substances containing vitamins, minerals, amino acids, or botanical concentrates for use by people to supplement the diet by increasing the total dietary intake.

10.5. Treatment Compliance

The IP, CBL-514, will be administered at the study site by the designated study staff under guidance of Investigator or designee.

If a participant’s IP administration and site-related procedures are not conducted as defined in the protocol, the Investigator must make note of ensuring compliance to the protocol for future activities. The date and time of each IP administration and accompanying activity will be recorded in the eCRF. The number of syringes administered will be documented in the participant’s source documents.

A dosing compliance less than 90% or more than 110% of total dosage per treatment is a major deviation and may be deemed to have an influence on PK. Effort should be made to adhere to the study design. Compliance is defined as the dosage administered out of the total dose or number of injections out of the amount required per treatment in accordance with protocol.

10.6. Blinding

Not applicable.

11. STUDY DRUG MATERIALS AND MANAGEMENT

11.1. Study Drug

The Sponsor will supply the IP to the investigational site. The IP provided for this study was manufactured under GMP and is suitable for human use.

11.2. Study Drug Packaging and Labeling

The Sponsor is responsible for the preparation, labeling and provision of details of batch numbers, safety, and stability data.

The IP will be labeled in accordance with local regulatory requirements and will be shipped at a temperature of 2°C to 8°C.

11.3. Study Drug Storage

Upon receipt, the IP must be stored at 4°C, with an allowed temperature range of between 2°C and 8°C. Appropriate storage conditions must be ensured by completing a temperature log in accordance with local requirements on a regular basis (e.g., by temperature logging devices that record every 30 minutes), showing minimum and maximum temperatures reached over the time interval. Refer to Pharmacy Manual for further details.

The Investigator or designee will be fully responsible for the security, accessibility, and storage of the IP while it is at the investigational facility.

11.4. Study Drug Preparation

CBL-514 is supplied as a ready-to-use solution. Each vial will contain an appropriate volume of CBL-514 with some surplus. Before administration to participants, the vials should be warmed up to room temperature. The solution of CBL-514 should be used before the expiry date.

Procedures relating to IP preparation and dispensing are outlined in the Pharmacy Manual.

11.5. Administration

A single course of CBL-514 will be administered as multiple subcutaneous injections on the abdomen. Oral analgesia as per standard of care will be administered to participants approximately 1 hour prior to IP administration. Topical anesthesia cream will be applied to the treatment area, followed by local anesthesia injection, both as per standard of care. If needed, participants may undergo ice compress immediately prior to IP injection. The IP administration should be completed within 60 minutes.

The Investigator or designee is responsible for the education of study staff as to the correct administration of the IP.

Details relating to IP administration are outlined in the Study Drug Administration Manual.

11.6. Study Drug Accountability

A record will be maintained by the investigational site that will account for all dispensing and return of any used and unused IP. At the end of the study, the IP will be reconciled, and a copy of the record given to the study monitor.

11.7. Study Drug Handling and Disposal

On completion of the study, any IP remaining at the investigational site will be returned to the Sponsor or its designee in accordance with the Sponsor's instruction. If the destruction of IP is allowed at the site according to the site procedure, any used or unused IP may be destroyed at the investigational site upon receipt of written approval from the Sponsor. Evidence of the destruction of any IP should be supplied to the study monitor and the Sponsor.

12. STUDY SCHEDULE

A Schedule of Assessments is provided in [Table 4](#).

Where possible, assessments should be conducted in order of least invasive to most invasive.

12.1. Visit 1: Screening (Day -28 to Day -1)

Prior to enrolling in the study, and before performance of any procedures, potential participants will attend a screening session at which time they will be provided with full information concerning details of the study assessments and procedures. They will also be provided with an ICF. Prior to being asked to sign the consent form, participants will be given time to review study information and ask any questions.

After the consent form is signed, screening assessments will be carried out as follows:

- [illegible]

¹ ECG to be performed in supine position after at least 5 minutes rest, prior to vital sign assessments.

- [REDACTED]

12.2. Visit 2: Baseline and Treatment (Day 1 to Day 2)

Visit 2 will involve an overnight stay at the study site (Day 1 to Day 2).

12.2.1. Day 1: Before Dosing

The following assessments will be carried out prior to the administration of IP unless otherwise noted¹:

- [REDACTED]
 - [REDACTED]
 - [REDACTED]
 - [REDACTED]
 - [REDACTED]
 - [REDACTED]
 - [REDACTED]
 - [REDACTED]
 - [REDACTED]
 - [REDACTED]
 - [REDACTED]
 - [REDACTED]
 - [REDACTED]
- [REDACTED]
 - [REDACTED]
 - [REDACTED]
 - [REDACTED]
 - [REDACTED]
 - [REDACTED]

¹ Available measurements of medical evaluations (body weight, abdominal fat thickness, physical examinations, and ECG) and laboratory evaluations (biochemistry, hematology, coagulation, and urinalysis) within 14 days prior to IP dose can be accepted as the Baseline value and will not necessitate duplicate examinations.

² If IP dose is within 7 days of Screening pregnancy test, pregnancy test on Day 1 will not be necessary to assess.

³ Blood samples for PK analysis will be collected from all 10 subjects. Of these 10 subjects, 6 subjects (the first 3 females and the first 3 males enrolled) will have additional blood samples collected for metabolite assessment.

— [REDACTED]
[REDACTED]
[REDACTED]

CBL-514 will be administered by assigned clinical staff. The IP administration should be completed within 60 minutes.

Participants will remain at the study site through to the completion of all scheduled post-dose procedures.

[illegible]

¹ Blood samples for PK analysis will be collected from all 10 subjects. Of these 10 subjects, 6 subjects (the first 3 females and the first 3 males enrolled) will have additional blood samples collected for metabolite assessment.

A participant who is withdrawn from the study due to a lack of dosing compliance will not continue with the collection of PK samples post-dose. Before discharge, physical examination, vital signs, and AE assessment will be performed, and a participant diary will be dispensed.

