8. INVESTIGATIONAL PLAN

8.1. Overall Study Design

This is a Phase 2 study to evaluate the safety, tolerability, PK and metabolite profile of CBL-514 injection at the maximal use dosage.

This Phase 2 study has an open-label and single course design. A total of 10 adult participants, composed of 5 females and 5 males, will be enrolled in a single cohort. Each participant will receive a single course of treatment with CBL-514 800 mg on the abdomen (administered as multiple subcutaneous injections) on Day 1 only.

Each participant will participate in the study for approximately 4 weeks, with a maximum expected duration of 61 days including up to 28 days for screening assessments, an Admission/Baseline visit on Day 1 with an overnight stay until Day 2, and 2 Follow-up visits (2 weeks [in-clinic] and 4 weeks [telephone] post treatment).

A schematic of the study design is provided in [Figure 1](#).

Study visits and assessments will occur as delineated in the Schedule of Assessments presented in [Table 4](#).

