9.2. Participant Exclusion Criteria

A participant who meets **any** of the following exclusion criteria must be excluded from the study:

1. Women of childbearing potential (WOCBP) who are not willing to commit to an acceptable contraceptive regimen from the time of Screening and throughout study participation until 90 days after the last IP dose, or who are currently pregnant or lactating. Male participants who are not willing to commit to an acceptable contraceptive method. For details on contraception, refer to [Section 9.3.3](#). Female participants who are not WOCBP are not required to use contraception.

* Not WOCBP is defined as females who have been surgically sterilized (hysterectomy or bilateral oophorectomy) or who are postmenopausal (defined as at least 50 years, with ≥ 12 months of amenorrhea) with a follicle-stimulating hormone (FSH) >40 IU/L prior to Screening.
2. Participant diagnosed with coagulation disorders or is receiving anticoagulant/antiplatelet therapy or medications or dietary supplements, which impede coagulation or platelet aggregation.
3. Participant has hemoglobin A1c (HbA1c) $\geq 9\%$, delayed wound healing, or any diabetic risks which, in the opinion of Investigator, is inappropriate to participate in the study.
4. Participant has a clinically significant cardiovascular disease and clinically significant abnormal findings in electrocardiogram (ECG).
5. Participant with active or prior history of malignancies within 5 years before Screening or being worked-up for a possible malignancy. Except adequately treated basal cell carcinoma of skin and in situ squamous cell carcinoma of skin would be eligible as per Investigator's discretion.

6. Participant with a history of human immunodeficiency virus (HIV)-1 infection, or participants with active HIV infection at Screening with positive HIV antigen/antibody (Ag/Ab) combo test.
7. Participants with any hepatic medical condition that, in the opinion of the Investigator, would compromise the participant's ability to undergo study procedures and/or interfere with the assessment of the obtained data.
8. Participants with a history of trypanophobia, the extreme fear of medical procedures involving injections or needles, or who experience vasovagal syncope and faint or pass out at the sight of blood or a needle.

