9.3.3. Contraception

Highly effective contraceptive methods with a failure rate of less than 1% per year when used consistently and correctly should be used. The list below is based on the recommendation of the Clinical Trial Facilitation Group (CTFG 2014).

- combined (estrogen and progestogen containing) hormonal contraception associated with inhibition of ovulation:
 - oral
 - intravaginal
 - transdermal
- progestogen-only hormonal contraception associated with inhibition of ovulation¹:
 - oral
 - injectable
 - implantable¹
- intrauterine device (IUD)¹
- intrauterine hormone-releasing system (IUS)¹
- bilateral tubal occlusion¹
- vasectomized partner^{1, 2}
- sexual abstinence³

¹ Contraception methods that in the context of this guidance are considered to have low user dependency.

² Vasectomized partner is a highly effective birth control method, provided that partner is the sole sexual partner of the WOCBP trial subject and that the vasectomized partner has received medical assessment of the surgical success.

³ In the context of this guidance sexual abstinence is considered a highly effective method only if defined as refraining from heterosexual intercourse during the entire period of risk associated with the study treatments. The reliability of sexual abstinence needs to be evaluated in relation to the duration of the clinical trial and the preferred and usual lifestyle of the subject. Periodic abstinence (calendar, symptothermal, post-ovulation methods) and withdrawal (coitus interruptus) are not acceptable methods of contraception. This is applicable for both female and male subjects.

- condom used by male partner during sexual intercourse.

Contraceptive requirements for male participants with WOCBP partner: A male participant should use condom during heterosexual intercourse and avoid sperm donation from the time of the first dose of IP, throughout study participation until 12 weeks after the last IP dose. For the WOCBP partner, contraception recommendations should also be considered.

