14.1.7.6. Pregnancy Testing

All WOCBP will be tested for pregnancy by a serum beta human chorionic gonadotropin (β -hCG) test pregnancy test at Screening. Urine β -hCG strip pregnancy testing will be performed for all other scheduled visits. Additional tests will be performed if a participant reports a risk of being pregnant anytime during the study.

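### Footnote 2 of Section 12.2.1 allows dosing on a Screening pregnancy test up to 7 days old, an exception that Section 6.4 does not state

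*Combined protocol and SAP*

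**What the plan says.** The protocol deals with pregnancy testing before dosing in several places.

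- **Section 12.2.1, footnote 2:** "If IP dose is within 7 days of Screening pregnancy test, pregnancy test on Day 1 will not be necessary to assess". The test becomes optional; it is not forbidden.
- **Section 6.4 (Participant Population):** a WOCBP has to show negative tests on two occasions, at Screening and before she receives the investigational product (IP). No exception is given.
- **Section 14.1.7.6 (Pregnancy Testing):** the Screening test is serum beta-hCG. After that, a urine "strip pregnancy testing will be performed for all other scheduled visits". No 7-day exception is given. The section adds a safeguard: "Additional tests will be performed if a participant reports a risk of being pregnant anytime during the study".
- **Section 14.4 (Pregnancy):** WOCBP are told to contact the Investigator at once if they suspect pregnancy, with a missed or late period as the example. Testing follows the Schedule of Assessments.
- **Section 9.2, criterion 1:** current pregnancy excludes. So does unwillingness to "commit to an acceptable contraceptive regimen from the time of Screening and throughout study participation until 90 days after the last IP dose".
- **Section 12.1:** Screening may fall on any day from Day -28 to Day -1.

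The Day 1 procedure list and the rows of Table 4 are redacted, so nothing is inferred from them. The footnote is legible and in force.

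**The concern.** The waiver applies to the women who have had the least time under required contraception. A WOCBP screened 8 to 28 days before dosing falls outside it and is retested on Day 1. One screened 1 to 7 days before dosing need not be. If she conceived shortly before Screening, the serum test may have been too early to show it, and no further scheduled test has to come between that result and the dose.

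The protocol treats exposure in pregnancy as something to avoid: it excludes pregnant women and requires contraception until 90 days after the dose. There is one dose, on Day 1, and it cannot be taken back. A site reading the legible text also finds Section 6.4 asking for testing on two occasions and a footnote that allows one. The issue is participant safety and consistency between sections. The pharmacokinetic (PK) endpoints and analysis populations are not touched.

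**Working it through.** **Which women fall under the waiver.** Let s be the days from the Screening serum test to the dose. Section 8.1 gives a "maximum expected duration of 61 days including up to 28 days for screening assessments". With follow-up ending on Day 29 + 4 = Day 33, 28 + 33 = 61, so there is no Day 0. Day -1 is then s = 1 and Day -7 is s = 7. The waiver covers Screening tests on Day -7 to Day -1, which is 7 of the 28 screening days.

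**The sections side by side.**

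| Section | Test before dosing if s is 1 to 7 |
|---|---|
| 6.4 | Required at Screening and again before IP |
| 14.1.7.6 | Urine strip at the other scheduled visits; Day 1 is Visit 2 |
| 12.2.1, footnote 2 | Day 1 test not needed |

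The conflict with Section 6.4 is the clearer one and needs no assumption about assays.

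**What a Day 1 strip would add.** The documents give no detection limit for either test, so two lags are assumed:

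- L = days from conception to a positive serum test: 8, 10 or 12.
- d = extra days before a urine strip turns positive: 0, 2 or 4.

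Conception dates before Screening that the serum test cannot show = L.

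Dates that a Day 1 strip recovers = min(L, max(0, s - d)). Dates left = L minus recovered. Share = recovered / L.

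A conception after Screening cannot show on the strip when s is 7 or less, because the shortest L + d is 8 days. Counting dates before Screening is therefore enough.

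Worked ends of the range at s = 7:

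- Best case, L = 8 and d = 0: recovered = 7, left = 1, share = 7/8 = 88%.
- Worst case, L = 12 and d = 4: recovered = 3, left = 9, share = 3/12 = 25%.

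| s (days) | Recovered | Left | Share | Current rule |
|---|---|---|---|---|
| 1 | 0 to 1 | 7 to 12 | 0% to 13% | test waived |
| 4 | 0 to 4 | 4 to 12 | 0% to 50% | test waived |
| 7 | 3 to 7 | 1 to 9 | 25% to 88% | test waived |
| 8 | 4 to 8 | 0 to 8 | 33% to 100% | strip done |
| 16 or more | all | 0 | 100% | strip done |

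For s = 1 to 7, a woman who has no Day 1 test recovers 0 dates. The shares count conception dates. They are not probabilities of pregnancy.

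**How many women.** Five females are planned. Section 9.5 adds to this: "Participants who are enrolled but who do not receive any IP will be replaced", and the Sponsor may recruit further participants. Only WOCBP with s of 7 or less count, and not those already protected before Screening by a listed long-acting or permanent method such as "bilateral tubal occlusion". The number may be zero.

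**The case against.** **The sections can be reconciled.** The phrase about all other scheduled visits in Section 14.1.7.6 cannot be literal, because Visit 4 is a telephone call at which staff cannot run a strip. It is a general statement, and a specific rule at the visit concerned would ordinarily govern. This stands in part: the conflict with Section 14.1.7.6 is soft. It does not dispose of Section 6.4. One could say that a Screening test is itself before dosing, but that section names two occasions and the footnote reduces them to one.

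**Other safeguards exist.** Section 14.1.7.6 adds a test when a risk is reported, and Section 14.4 asks women to report suspected pregnancy. Both stand and both narrow the gap. They do not help a woman who suspects and reports nothing, which is possible with a conception too recent for a missed period.

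**Seven days is a reasonable age for a result.** Footnote 1 of Section 12.2.1 accepts several other baseline measurements up to 14 days old, and nothing in the documents shows 7 days to be unacceptable for this test. That is fair, and it is a reason for low priority. But those measurements do not share the problem of a pregnancy too early to detect.

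**The strip does little.** On the same assumed lags, zero benefit lies within the range at 1 and 4 days, and some dates stay undetected even at 8 days, where the protocol already tests. This stands. Much of the gap is a limit of hCG testing close to conception.

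**Conclusion.** The point holds as a small safety and consistency matter. Footnote 2 lets a WOCBP be dosed on one serum result up to 7 days old. Section 6.4 states no such exception, and neither does Section 14.1.7.6, although that second conflict is weaker.

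At most 5 planned women plus replacements or added participants are concerned, possibly none. The absolute chance of such a pregnancy is small and is not given in the documents. The gain from a Day 1 strip (25% to 88% of missed dates at 7 days, 0% to 50% at 4 days, 0% to 13% at 1 day) rests wholly on the assumed lags.

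A reader might infer more than this, and the documents do not support it:

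- *That the protocol accepts dosing pregnant women or bars the Day 1 test.* Current pregnancy excludes, and the footnote only makes the test optional.
- *That women under the waiver have no other protection.* Sections 14.1.7.6 and 14.4 both provide for reported risk or suspicion.
- *That a Day 1 strip would close the gap.* Between 1 and 9 conception dates remain undetected at 7 days, and 7 to 12 at 1 day.
- *That Table 4 omits or contradicts the test.* Its rows are redacted. A repeat of the waiver there would not resolve the conflict with Section 6.4.

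**What to change.** Delete footnote 2 in Section 12.2.1, and any repeat of it in Table 4. Add to Section 14.1.7.6, in line with Section 6.4: *Every WOCBP will have a urine beta-hCG strip test on Day 1 before dosing, whatever the date of the Screening test. IP will be given only if the result is negative.*

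If the sponsor prefers to keep the waiver, the exception should at least be stated and justified in Sections 6.4 and 14.1.7.6, so that a site knows which rule governs. That repairs the inconsistency but leaves the safety gap as it is.

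The cost of the preferred change is one urine strip per affected woman at a visit she already attends, one footnote deleted and two sentences added. It needs no extra visit and does not affect PK sampling. Priority is low.
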